12. ANCILLARY ENDPOINT ANALYSES

Whenever a Statistical test is performed for a Ancillary Endpoint, it is of hypothesis generating and descriptive in nature.

12.1. CAPTURE CYCLES AND NON-CAPTURE CYCLES OF RIGHT VENTRICULAR PACING ELECTROGRAMS

Right ventricular pacing electrograms will be collected and analyzed to identify right ventricular capture and non-capture beats and to assess a right ventricular threshold determination method on Platinium Implantable Cardioverter Device (ICD).

The analysis is based on RV electrogram strips. Each subject will have 4 electrograms recorded: at 5V, 2V; 1.5V and 1V RV pacing test. Each electrogram is a 20 sec EGM recording, that is, 20 sec of cardiac beat. Each RV electrogram is composed of cardiac beat cycles; each of them can results in capture or non-capture of the right ventricle depolarization .

The number and percentage of accurate captures (accurate discrimination between capture/non-capture cycles) based on all cycles will be presented by RV pacing configuration (RV-P test and RV-A test) and by visit. A 95% CI will be presented.

Barplots for the same will be provided.

This will also be listed by subject.

This analysis will be based on AP.

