3.3. ANCILLARY ANALYSIS

Right ventricular pacing electrograms might be collected and analyzed to identify right ventricular capture and non-capture beats and to assess a right ventricular threshold determination method on Platinium Implantable Cardioverter Device (ICD).

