4.1.4. Ancillary endpoint

Right ventricular pacing electrograms might be collected and analyzed to identify right ventricular capture and non-capture beats and to assess a right ventricular threshold determination method on Platinium Implantable Cardioverter Device (ICD).

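### The single pooled accuracy figure for the right-ventricular analysis (SAP 12.1) cannot by itself show that the method detects loss of capture

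*SAP*

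**What the plan says.** Protocol 4.1.4 gives the ancillary endpoint two parts: "to identify right ventricular capture and non-capture beats and to assess a right ventricular threshold determination method". Protocol 3.3 and SAP 2.1.3 give the same two parts as the objective, and SAP 12.1 repeats them.

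SAP 12.1 fixes the recordings: "Each subject will have 4 electrograms recorded: at 5V, 2V; 1.5V and 1V RV pacing test". On their length it says "Each electrogram is a 20 sec EGM recording, that is, 20 sec of cardiac beat", and it notes that each cycle may or may not capture. The planned statistic is: "The number and percentage of accurate captures (accurate discrimination between capture/non-capture cycles) based on all cycles will be presented by RV pacing configuration". Results are also split by visit and come with a 95% confidence interval, bar plots and a listing by subject.

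SAP 12.1 does not contain:
- a split by amplitude, or by whether the beat truly captured;
- a count of non-capture beats, or of the subjects who supply them;
- a named reference for true capture;
- an RV threshold derived by the method, or a comparison with a measured one.

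Related sections do not fill these gaps. The Ancillary Population (SAP 6.6) needs only one RV electrogram. SAP 8.2 summarises RV pacing threshold but is not linked to 12.1. SAP 12.2, the only other ancillary analysis, concerns LV vector tests. SAP 13.1 plans sensitivity and specificity, but only for high LV thresholds. Protocol section 11 describes independent adjudication of LV threshold values only.

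**The concern.** Reading a threshold depends on recognising the beats that fail to capture. No strip is recorded below 1 V, so a subject whose RV threshold is 1 V or less should capture in all four strips. That subject supplies no non-capture beats. When such subjects are pooled with the others and all beats share one denominator, capture beats can dominate the percentage. A method that never recognises loss of capture could then report a high accuracy.

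Calling a non-capture beat capture is also the error that leads to an underestimated threshold. For the LV feature, the protocol lists underestimation among the main risks (7.1) and the SAP analyses it separately (11.1 B). The RV figure mixes that error with the opposite one. At stake is whether the reported percentage can support any statement about RV loss-of-capture detection or RV threshold determination.

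**Working it through.** The documents state no sample size, target or performance goal for the RV analysis, so there is no planned figure to reproduce. The check asks what score a rule with no discriminating ability would get.

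**Inputs from the documents.** Four amplitudes (5, 2, 1.5 and 1 V), strips of 20 seconds, and one accuracy over all cycles within each RV configuration and visit (SAP 12.1).

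**Assumptions.** A strip at amplitude V captures throughout if V is at or above the subject's threshold T, and fails throughout otherwise. Every strip has the same number of beats. The share of subjects at each threshold is not in the documents, so it is varied.

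**Step 1: one subject.** For a rule that always calls capture, accuracy = (number of the four amplitudes at or above T) / 4.

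| RV threshold T | Strips that capture | Strips that do not | Accuracy of the rule |
|---|---|---|---|
| T ≤ 1 V | 4 | 0 | 4/4 = 100% |
| 1 < T ≤ 1.5 V | 3 | 1 | 3/4 = 75% |
| 1.5 < T ≤ 2 V | 2 | 2 | 2/4 = 50% |
| 2 < T ≤ 5 V | 1 | 3 | 1/4 = 25% |

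**Step 2: pooled over subjects.** Let f be the share of subjects with T ≤ 1 V, put the rest in one higher band, and let a be that band's accuracy from step 1. Pooled accuracy = f + (1 − f) × a.

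| f | Rest at >1 to 1.5 V (a = 0.75) | Rest at >1.5 to 2 V (a = 0.50) | Rest at >2 to 5 V (a = 0.25) |
|---|---|---|---|
| 20% | 80% | 60% | 40% |
| 50% | 87.5% | 75% | 62.5% |
| 90% | 97.5% | 95% | 92.5% |

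For example, 0.20 + 0.80 × 0.75 = 0.80, and 0.90 + 0.10 × 0.25 = 0.925.

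**Step 3: what one figure conceals.** Take f = 80% with the rest at >1 to 1.5 V. Capture beats make up 0.80 + 0.20 × 0.75 = 95% of all beats and non-capture beats 5%. The always-capture rule scores 95%. A method that recognises every non-capture beat, and gets a proportion x of capture beats right, has the same score when 0.95x + 0.05 = 0.95, so x = 0.90/0.95 = 94.7%. One method detects all loss of capture and the other none, yet the pooled percentage is the same.

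**Step 4: the same rule with the beats separated.** Always calling capture gives 100% on capture beats and 0% on non-capture beats, whatever the threshold mix. The second rate exposes the failure. In subjects with T ≤ 1 V that rate has no denominator, and their threshold can only be placed at or below 1 V.

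**The case against.** The strongest objection is about weight. Protocol 3.3 and 4.1.4 say only that RV electrograms might be collected. Protocol 8.5.2 treats ancillary endpoints descriptively, SAP section 12 calls any ancillary test hypothesis generating, and there is no RV success criterion. All of this stands and limits the point to a minor one.

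The plan also gives the reader some help. SAP 8.2 summarises RV threshold at all visits, and SAP 17.2 includes median and quartiles, so one can judge roughly how many subjects lie at or below 1 V. SAP 12.1 lists results by subject, and SAP 17.1 lists all collected and derived data. This makes a later split possible but does not plan one, and the 8.2 summary uses the Evaluable Population rather than the Ancillary Population.

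Three stronger readings are tempting, and the documents do not support them:
- **That the ancillary objective goes unanswered.** Subjects with thresholds above 1 V do supply non-capture beats, so the beat-discrimination part gets an answer, though a weak one. Only the threshold part lacks a planned endpoint in 12.1.
- **That the reported percentage is bound to be inflated.** With few subjects at or below 1 V and the rest well above it, the always-capture rule scores poorly (40% in the lowest case shown). Capture may also be intermittent within a strip, which the all-or-none model ignores.
- **That no beat-level specification exists anywhere.** SAP 17.8 refers to a separate document on extraction and analysis of the device files, and to a metadata file. Neither is available here, and either could define reference and amplitude variables. What can be said is that SAP 12.1 does not plan the split.

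**Conclusion.** The point holds as a minor one. The per-subject scores follow directly from the four amplitudes, given stable capture above threshold and equal beats per strip. The pooled range of 40% to 97.5% also depends on an assumed threshold mix, so the size of any inflation in this trial is unknown. The main conclusion does not need that size: without knowing how many non-capture beats lie behind it, a pooled percentage cannot separate a method that detects loss of capture from one that does not. The RV threshold half of the objective has no endpoint in SAP 12.1. The primary and secondary LV conclusions are unaffected.

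**What to change.** In SAP 12.1, for each RV configuration and visit:

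- Report two headline rates: the proportion of reference-capture beats called capture, and the proportion of reference-non-capture beats called non-capture. Give the numbers of beats and of subjects behind each.
- Name the reference that defines true capture.
- Keep the pooled accuracy as a secondary line.
- Report how many subjects have at least one non-capture recording. State that in the others the data can show only a threshold at or below 1 V and any false non-capture calls.
- Do not exclude those other subjects. A false non-capture call in one of them would wrongly place the threshold above 1 V, and dropping them would hide that overestimation.

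The cost is SAP wording and one extra table from the planned recordings; no amplitude or procedure changes. The downside is that the non-capture rate may rest on few subjects and have a wide interval, but that would reflect the evidence available.

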8.5.2. Secondary and ancillary endpoints

Secondary and ancillary endpoints will be assessed at all follow-ups using descriptive statistics. Point estimates and 95% CI will be presented wherever possible.

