6.6. ANCILLARY POPULATION (AP)

The Ancillary Population (AP) consists of all subjects in IP with at least one right ventricular pacing electrogram collected at the M0 or M1 visit.

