10. SECONDARY EFFICACY ANALYSES

Secondary and Ancillary endpoints will be assessed at all visits using descriptive statistics. Point estimates and exact CI (Clopper & Pearson, 1934) will be presented wherever possible.

Whenever a Statistical test is performed for a Secondary Endpoint, it is of hypothesis generating and descriptive in nature.

10.1. ASSESSMENT OF DIAGNOSTIC ACCURACY OF “IN-CLINIC LVAT” TEST AT M0 VISIT: INDEPENDENT REVIEWER VALIDATION OF LV THRESHOLD VALUE PROVIDED BY ALGORITHM

This endpoint is the number of accurate determination of the LV pacing threshold value provided by the algorithm feature and an independent reviewer, on all LV pacing vectors and all pacing configurations available at M0 visit.

Diagnostic accuracy is defined as an accurate adjudication by an independent reviewer of LV threshold value provided by the algorithm. The adjudication is based on capture and loss of capture analysis on electrogram strips recorded and stored during “In-Clinic LVAT” tests. The LV threshold value provided by the algorithm compared to the reviewer adjudication is considered accurate if the difference is within ± 1 step (meaning ± 0.25 V if threshold < 2.5V, else ± 0.5 V as measured). The definition of an Accurate LV threshold value is provided above in Table 5.

In case the algorithm and the reviewer adjudication provide both a LV threshold value equal to “>5V” (the LV vector test has resulted in “no capture” or “threshold value higher than 5V at starting amplitude), the LV threshold value is considered accurate. Number and percentages of “accurate” and “inaccurate” matches will be presented along with the exact 95% CI (Clopper & Pearson, 1934).

This analysis will be performed on M0-ITT population.

Decomposition of Diagnostic Accuracy by LV Vector and by LV pacing configuration

Total number of attempted, completed, and accurate LV vector tests will be presented by LV vector for each LV pacing configuration.

For the LV tests performed for subjects with either IS1 and IS4 leads (six LV vectors common to IS1 and IS4), the percentage for the number of LV vector tests “attempted”, will be calculated based on the number subjects implanted with either IS1 and IS4 leads.

For the LV tests performed for patients with IS4 leads (eight LV vectors pertaining only to IS4), the percentage for the number of LV vector tests “attempted”, will be calculated based on the number of patients implanted with IS4 lead.

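### Under the SAP's default method, the 95% CI for right-ventricular capture accuracy treats heartbeats as independent, so it is too narrow by an amount that depends on an unstated within-subject correlation

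*SAP*

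**What the plan says.** SAP 12.1 assesses how well capture and non-capture beats are told apart on right-ventricular electrograms. On the material per subject it says "Each subject will have 4 electrograms recorded: at 5V, 2V; 1.5V and 1V RV pacing test", and on strip length "Each electrogram is a 20 sec EGM recording, that is, 20 sec of cardiac beat". The result is the number and percentage of accurate captures, "based on all cycles will be presented by RV pacing configuration (RV-P test and RV-A test) and by visit. A 95% CI will be presented". Results are also to be listed by subject. The population is defined in SAP 6.6: "The Ancillary Population (AP) consists of all subjects in IP with at least one right ventricular pacing electrogram collected at the M0 or M1 visit". Its size is not stated.

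SAP 12.1 does not name the interval method. The general rule opens SAP section 10: "Secondary and Ancillary endpoints will be assessed at all visits using descriptive statistics". The next sentence reads "Point estimates and exact CI (Clopper & Pearson, 1934) will be presented wherever possible". Protocol 8.5.2 says only "Point estimates and 95% CI will be presented wherever possible". Neither document mentions correlation between beats of the same subject or strip, a cluster-adjusted interval, or a subject-level estimate for this endpoint. SAP section 12 adds "Whenever a Statistical test is performed for a Ancillary Endpoint, it is of hypothesis generating and descriptive in nature".

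**The concern.** A Clopper-Pearson interval is valid when each trial is an independent draw with the same success probability. Here the trial is a heartbeat. The beats of one strip share a heart, a lead and a pacing output, and a subject's strips share the heart and the lead. If a subject's signal shape leads the method to misclassify one beat, it is plausible that other beats of that subject are misclassified too. The independent units are the subjects, of whom there are a few dozen. The planned interval would be computed on several thousand cycles.

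At stake is the stated precision of the only result in the plan on right-ventricular capture discrimination. A reader deciding whether the method merits further work would see a tight interval that the number of subjects may not support.

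**Working it through.** **What can be reproduced.** The documents give no number of cycles, accuracy, correlation or interval width for this endpoint, so there is no plan figure to reproduce. The only subject counts are in SAP 2.3: 47 evaluable, and 47/(1 − 0.2) = 58.75, rounded up to 59 enrolled. They were derived for the left-ventricular primary endpoint.

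**Inputs.**
- From SAP 12.1: 4 strips of 20 s per subject; all cycles pooled by configuration and visit.
- From SAP section 10: exact Clopper-Pearson interval.
- Assumed: heart rate 60 to 100 per minute; the 4 strips are per configuration and visit; 47 subjects; ICC varied from 0.01 to 0.30; accuracy 95% for the worked example.

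**Beats per subject.** m = 4 × 20 s × rate/60, which is 80 at 60/min and 133 at 100/min.

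**Width ratio.** The design effect is DE = 1 + (m − 1) × ICC. The correct interval is wider than the all-cycles interval by about √DE. For m = 80 and ICC 0.05, DE = 1 + 79 × 0.05 = 4.95 and √4.95 = 2.2.

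| ICC | DE, m = 80 | √DE | DE, m = 133 | √DE |
|---|---|---|---|---|
| 0.01 | 1.79 | 1.3 | 2.32 | 1.5 |
| 0.02 | 2.58 | 1.6 | 3.65 | 1.9 |
| 0.05 | 4.95 | 2.2 | 7.62 | 2.8 |
| 0.10 | 8.90 | 3.0 | 14.2 | 3.8 |
| 0.20 | 16.8 | 4.1 | 27.5 | 5.2 |

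The ratio does not depend on the number of subjects, which only moves the absolute width. Turned round, a factor of 2 needs an ICC of about 0.02 to 0.04, and a factor of 3 needs about 0.06 to 0.10.

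**Example.** With 47 subjects and m = 80 there are 47 × 80 = 3,760 cycles. At 95% accuracy the all-cycles Clopper-Pearson interval is 94.3% to 95.7%. Replacing n by n/DE gives:
- ICC 0.05 (effective n 3,760/4.95 = 760): 93.2% to 96.4%
- ICC 0.10 (effective n 3,760/8.9 = 422): 92.5% to 96.9%
- ICC 0.30 (DE 24.7, effective n 152): 90.2% to 97.9%

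**Coverage.** A beta-binomial simulation (20,000 runs, 47 subjects, m = 80, true accuracy 95%) gives actual coverage of the nominal 95% interval of 87% at ICC 0.01, 63% at 0.05 and 50% at 0.10.

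**Other reading of the four strips.** If four is a subject's total over two configurations and two visits, each cell averages one strip, or 20 to 33 beats. The ratio is then about 1.4 to 1.6 at ICC 0.05, 1.7 to 2.1 at 0.10 and 2.6 to 3.3 at 0.30.

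**The case against.** SAP 12.1 does not itself prescribe an independence-based interval. The phrase about all cycles describes the count and percentage, and the sentence on the CI names no method, whereas SAP 12.2 specifies an exact CI. This is true of 12.1 read alone. But the section 10 sentence expressly covers ancillary endpoints, so a programmer following the SAP would compute Clopper-Pearson on cycles. If the method were really open, the SAP would still need to name one.

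The endpoint is ancillary and descriptive. Protocol 3.3 and 4.1.4 say only that these data might be collected. There is no right-ventricular hypothesis, performance goal, sample size or decision rule. All of this stands and limits how much the point matters. The disclaimer in SAP section 12, however, concerns statistical tests, and a confidence interval is still a statement about precision.

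Results will be listed by subject, so variation between subjects will be visible to anyone who reads the listing. That helps, but it does not correct the printed interval.

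A reader might go further and infer that the interval is several times too narrow as a matter of fact. The documents do not support that. They give no correlation and no heart rate, do not say whether the four strips are per configuration and visit, and do not give the size of the ancillary population. At an ICC of 0.01 to 0.02 the shortfall is only 1.3 to 1.9 times. Nor do they show that beats within a strip are nearly identical.

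**Conclusion.** The point holds in a conditional form. As written, SAP 12.1 read with section 10 produces an interval that ignores repeated beats from the same subject, and it is too narrow under any positive within-subject correlation. The direction is not in doubt; the size is. With 80 to 133 beats per subject per configuration and visit, it runs from about 1.3 to 1.5 times too narrow at ICC 0.01 to about 4.1 to 5.2 times at 0.20, and less if the four strips are a subject's total.

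It would be wrong to read this as invalidating the reported percentage: correlation affects the interval, and the pooled percentage remains a valid description of the observed cycles, though subjects with more beats weigh more. The primary endpoint uses different data and is not touched. The error bars are nevertheless wrong as planned and cheap to correct, so the SAP should be changed.

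**What to change.** In SAP 12.1, replace the default exact interval with a 95% CI that takes the subject as the cluster, for each right-ventricular configuration and visit. A subject-level bootstrap or GEE with robust variance would do. Clustering on the subject also covers correlation within a strip. In the same table, report the number of subjects as well as the number of cycles, and summarise accuracy per subject (for example median, quartiles and range). State in the text whether the four strips are per configuration and visit.

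The cost is a few lines of SAP text and a little more analysis code, with no new data, since results are already to be listed by subject. The interval will be wider. If very few subjects have any misclassified beats, both methods can become unstable; the per-subject summary then carries most of the information.

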12.2. SUCCESS-RATE BASED ON SUBJECTS

A subject will be considered “success” if there is at least one LV vector test successful among all LV vector tests performed for all LV pacing configurations in either of the two subject visits.

The number and percentage of “successful” and “unsuccessful” subjects will be presented. 95% exact CI will be provided.

Only subjects with non-missing manual data will be considered.

This analysis will be based on ITT.

13. ADDITIONAL EXPLORATORY ANALYSIS

Whenever a Statistical test is performed for an Additional Analysis, it is of hypothesis generating and descriptive in nature.

13.1. ACCURATE DETERMINATION OF HIGH PACING THRESHOLD VALUE (NO CAPTURE OR >5V) : ALGORITHM Vs. INDEPENDENT REVIEWER

All LV vector tests are done at a starting amplitude of 5V for all LV pacing configurations. Therefore, if the LV threshold value is > 5 V or if there is no capture at the starting amplitude for the tested LV vector, then the algorithm identifies the LV threshold value as a high pacing threshold “> 5V”.

Number and percentage of correct determination of high pacing threshold value (>5V) provided by the algorithm feature and an independent reviewer, on all LV pacing vectors and all LV pacing configurations available at M0 visit will be presented. Percentage will be based on all subjects included in the M0-ITT.

A Fisher exact test will be performed to test the significance of association between accurate determination provided by the algorithm feature and the independent reviewer. The two-sided p-value will be presented.

In addition, the Sensitivity and Specificity as defined below will also be presented:

i. Sensitivity or Probability (Algorithm feature = High Pacing Threshold | Independent reviewer = High Pacing Threshold) = $TP/(TP+FN)$

i. Specificity or Probability (Algorithm feature = Not High Pacing Threshold | Independent reviewer = Not High Pacing Threshold) = $TN/(FP + TN)$

13.2. ASSESSMENT OF CONSISTENCY OF “IN-CLINIC LVAT” TEST BETWEEN M0 AND M1 VISITS: COMPARISON TO MANUAL LV THRESHOLD TESTS RESULTS

At each of the two subject visits, success rate will be calculated for each LV vector and each LV pacing configuration based on M0-ITT and M1-ITT respectively. As we have up to 14 LV vectors and 3 configurations, we will have a total of 42 success rates at each M0 and M1 visits.

Null Hypothesis: The Success-rate for LV tests at M0 visit = The success rate for LV tests at M1 visit

LEVEA – Statistical Analysis Plan

Alternative Hypothesis: The Success-rate for LV tests at M0 visit \neq The success-rate for LV tests at M1 visit.

A paired t-test will be performed to test if the mean difference of the success rate over the two visits is significantly different from 0. A two-sided p-value will be presented. This will be performed by configuration and overall. The mean difference and its 95% CI will also be presented.

This analysis will be performed on ITT.

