6.3. INTENTION TO TREAT POPULATION (ITT)

The Intention To Treat (ITT) population consists of all subjects from EP with at least 1 eligible complete LV Vector Tests at M0 or M1 visit.

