6.4. M0- INTENTION TO TREAT POPULATION (M0-ITT)

The M0-Intention To Treat (M0-ITT) population consists of all subjects from ITT with at least 1 eligible complete LV Vector Tests at M0 visit.

LEVEA – Statistical Analysis Plan

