9.1.2. STATISTICAL TEST OF PRIMARY ENDPOINT

The Null hypothesis: Success rate of the “In-Clinic LVAT” feature $< 90\%$.

The alternative hypothesis: Success rate of the “In-Clinic LVAT” feature $\geq 90\%$.

Each LV vector test will be categorized as a success if the automatic and manual LV threshold test has an equivalent LV threshold value, and failure otherwise. The definition of an equivalent LV threshold value is provided above in Table 4.

The success rate of “In-Clinic LVAT” test is defined as: Number of successes/Total Number of completed LV vector tests (excluding the tests for which Manual test is missing).

A one-sided exact binomial test for proportion at 2.5% level of significance (alpha) will be performed to test the null hypothesis for the primary endpoint. The null hypothesis will be rejected if the p-value is less than 0.025.

The estimate of success rate and 95% exact CI (Clopper & Pearson, 1934) will be presented.

LEVEA – Statistical Analysis Plan

DECOMPOSITION OF PRIMARY ENDPOINT SUCCESS RATE BY LV VECTOR AND BY CONFIGURATION

Total number of completed and successful LV vector tests considered for the Primary Analysis will be presented by:

- i. LV vector tests considered with DDD A-test LV pacing configuration at M0 visit. The break up of the five LV vectors will also be presented.
- ii. LV vector tests considered with VVI test LV pacing configuration at M0 visit. The break up of the five LV vectors will also be presented.
- iii. LV vector tests considered with DDD A-test LV pacing configuration at M1 visit. The break up of the five LV vectors will also be presented.
- iv. LV vector tests considered with VVI test LV pacing configuration at M1 visit. The break up of the five LV vectors will also be presented.

Only those LV tests will be considered for which manual tests are non-missing. For number of LV vector tests “completed”, the percentage will be calculated based on ITT.

For number of LV vector tests “Successful”, the percentage calculated based on number of LV vector tests “completed”.

All LV vector test results will be listed.

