10.4. EVALUATION OF THE APPLICABILITY OF THE ALGORITHM

The algorithm may not be applicable to some subjects, mainly because of a very long inter-ventricular conduction delay (VV delay). A subject is defined as “eligible” if he/she has at least one complete LV vector test in either of the M0 or M1 visit.

The endpoints for the applicability of the algorithm in the population are:

- A. The number and percentage of subjects who are “eligible” to receive the algorithm. Percentage will be calculated based on the total number of subjects included in the EP, that is:

Number of subjects with at least one complete LV Vector Test at M0 or M1 visits/ Total Number of subjects in EP.

- B. For subject having IS1 lead, up to 6 LV vector tests over 3 LV pacing configurations will be attempted for each subject at each visit.

Among all the subjects having IS1 leads, the number and percentage of subjects having no, one, two,..., six Attempted, Completed and Successful LV vector tests will be presented by LV pacing configuration and visit.

Among all the subjects having IS4 leads, the number and percentage of subjects having one, two,..., fourteen Attempted, Completed and Successful LV vector tests will be presented by LV pacing configuration and visit.

Only subjects with non-missing manual data will be considered.

Percentages calculated based on the number of subjects in EP with the respective lead and configuration will be presented for Attempted, Completed and Successful LV tests.

This information will also be presented with the help of histograms.

This analysis will be based on EP.

This will also be listed.

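### SAP 13.1 and the total rows of the SAP 9.1.2 decomposition divide counts of LV vector tests by numbers of subjects, so the percentages are not proportions and can exceed 100%

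*SAP*

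**What the plan says.** **SAP 13.1.** Correct determinations of a high pacing threshold by the algorithm, judged against the independent reviewer, are counted "on all LV pacing vectors and all LV pacing configurations available at M0 visit will be presented". The base follows: "Percentage will be based on all subjects included in the M0-ITT". SAP 6.4 defines that set in subjects: it "consists of all subjects from ITT with at least 1 eligible complete LV Vector Tests at M0 visit".

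**SAP 9.1.2, decomposition of the primary endpoint.** "Total number of completed and successful LV vector tests considered for the Primary Analysis will be presented by" four combinations: DDD A-test and VVI at M0, then the same two at M1. Each total is also broken down into the five primary vectors. For completed tests, "the percentage will be calculated based on ITT". SAP 6.3 defines ITT in subjects as well: it "consists of all subjects from EP with at least 1 eligible complete LV Vector Tests at M0 or M1 visit". The next sentence of 9.1.2 bases the successful count on the number of completed tests.

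**General rule.** SAP 17.2 takes the number of subjects in the population as the reference unless an exception is specified. Neither section specifies one for these percentages.

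**The concern.** Each subject contributes several tests to the numerator and only one unit to the denominator. The quotient is an average number of tests per subject, printed as a percentage.

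In 13.1 this misleads even below 100%. Suppose all subjects have IS1 leads, all tests are done, and 3% of tests are truly high and correctly called high. The printed figure is 0.03 x 18 = 54% correct determination, although the algorithm made no error. The figure follows how common high thresholds are and how many vectors were tested, not accuracy.

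In the 9.1.2 totals, the reader cannot tell what share of the primary data came from the preferred configuration and what share from the fallbacks, which is the purpose of that table.

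**Working it through.** **1. The plan's own figures (SAP 2.3).** Inputs: null rate 90%, expected rate 95%, one-sided alpha 2.5%, power 80%, five vectors per subject, attrition 20%. With an exact binomial test at n = 231, the rule is at least 217 successes, with exact alpha 0.0239 and power 81.6%. Then 231/5 = 46.2, rounded up to 47 subjects, and 47/(1 - 0.20) = 58.75, rounded up to 59. All three figures reproduce. The SAP states no value for the percentages at issue.

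**2. 9.1.2 total rows.** Protocol 4.1.2 allows one test per vector per subject in the primary analysis, so a total row holds at most 5 tests per subject.

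- Ceiling: 5 x 47 / 47 = 500%.
- All planned tests in the M0 DDD A-test row, which SAP Table 8 prefers: 231/47 = 491.5%. If ITT held 59 subjects: 231/59 = 391.5%.
- Most even split of 231 tests over four rows: 231/4 = 57.75, so the largest row holds at least 58 tests. With 47 ITT subjects that row shows at least 58/47 = 123%. With 59 it could be as low as 58/59 = 98%, so exceeding 100% is then not forced.
- Per-vector rows: at most one test per subject, so at most 100%.

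**3. 13.1, tests per subject at M0.** For IS1, SAP 10.4 gives "up to 6 LV vector tests over 3 LV pacing configurations will be attempted for each subject at each visit", so 6 x 3 = 18. For IS4, SAP 13.2 says "As we have up to 14 LV vectors and 3 configurations", so 14 x 3 = 42.

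Let m be the tests per subject and r the share of tests that are correct high calls. The printed percentage is 100 x r x m, and it passes 100% when r > 1/m. The number of subjects cancels. The documents give no value for r, so the rates below are assumptions, with full testing:

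| Lead mix | m | r at which 100% is passed | r = 5% | r = 10% | r = 20% |
|---|---|---|---|---|---|
| All IS1 | 18 | 5.6% | 90% | 180% | 360% |
| Half IS4 | 30 | 3.3% | 150% | 300% | 600% |
| All IS4 | 42 | 2.4% | 210% | 420% | 840% |

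**4. With matching units.** For 9.1.2, 231 tests out of 5 x 47 = 235 possible is 98.3%. Each vector of a subject enters only one of the four rows, so the four shares together cannot exceed 100%. For 13.1, any percentage of adjudicated tests is at most 100%.

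**The case against.** **The phrases may only name the analysis population.** SAP 13.2 uses a similar phrase about M0-ITT and M1-ITT where it can only mean the source of the data, and the sentence in 13.1 is the only one there that names a population. This is the best argument on the other side. It does not fit the words of 13.1, which name all subjects, or the default in 17.2, or the next sentence of 9.1.2, which names tests when tests are meant. If it were accepted, the denominator would be undefined and the text would still need a change. The dataset specification that might settle the programming is a separate file not included with the SAP.

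**Subject bases are the SAP's own pattern.** This stands for per-vector rows. In 10.1, 10.2 and 11.1 the first count for each vector and configuration is taken over subjects, and later counts over tests. The change history in SAP 3.2 explains that attempted equals completed in the primary decomposition, so the attempted count was dropped and completed took the ITT base. A reader might infer that 9.1.2 breaches the SAP's convention throughout. The documents do not support that: the fault lies in carrying a sound per-vector base up to the totals.

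**No interval is at stake.** A reader might infer that the plan attaches an invalid confidence interval to the 13.1 percentage. It plans none there. The rule in SAP 10 on exact intervals covers secondary and ancillary endpoints, and 13.1 is exploratory.

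**The useful measures are already planned.** Sensitivity and specificity in 13.1 have proper denominators, and the raw counts will stand beside the 9.1.2 percentages. This limits the harm but does not make the stated percentages correct.

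**Conclusion.** The stated bases are wrong in two places: the percentage in 13.1 and the visit-by-configuration totals in 9.1.2. The 9.1.2 result rests on the SAP's own plan: up to 500%, and at least 123% in one row if 231 tests come from 47 ITT subjects. The 13.1 result depends on full testing, the lead mix and an assumed rate of correct high calls. At 5% with all IS1 leads it stays at 90%, but it is still not a proportion.

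A reader might infer that the primary conclusion is compromised. It is not. The success rate in 9.1.1 and 9.1.2 is successes over completed tests with a manual value, and its exact test and interval use the same base. This is a reporting error in one exploratory and one descriptive table. It should be corrected because the rule is wrong as written and the correction is cheap.

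**What to change.** **SAP 13.1.** State that the unit is the complete M0 LV vector test with a reviewer adjudication. Replace the percentage of subjects with two figures: correct high calls over reviewer-high tests, which is the planned sensitivity, and overall agreement, (TP + TN) over all adjudicated tests. Correct high calls over all adjudicated tests would not be enough, because that ratio mostly reflects how common high thresholds are.

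**SAP 9.1.2.** Keep ITT subjects as the base for the per-vector rows. For the total rows use 5 x ITT subjects, labelled as the share of planned primary tests supplied by that visit and configuration. It should not be called a completion rate: under Table 8, VVI and M1 tests enter only when the preferred test is unavailable, so low values in those rows are expected.

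**Cost.** A few sentences in the SAP and the matching table shells. No change to design, data collection or the primary analysis.
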